## 1 PROTOCOL SUMMARY

### 1.1 SYNOPSIS

#### Background

Proton pump inhibitors (PPIs) are among the most commonly prescribed medications in the Veterans Health Administration (VHA), accounting for over 11 million 30-day prescriptions and nearly \$50 million in medication costs annually. Though effective for treatment of acid-related disorders such as gastroesophageal reflux disease (GERD), PPIs have been associated with a number of possible harms in observational studies (e.g., enteric infections such as *Clostridium difficile* colitis, pneumonia, chronic kidney disease, fractures, dementia, and a recent VA study reported increased mortality in Veterans receiving PPIs). Unfortunately, PPIs continue to be used without an appropriate indication or for longer and at higher doses than necessary. Accordingly, in September 2019, VHA Pharmacy Benefits Management Services (PBM) deployed the Randomized PPI De-Prescribing (RaPPID) Program – a national, multi-level PPI de-prescribing initiative targeting patients for whom chronic PPI therapy may not be necessary. This program, modeled after a successful initiative in one Veterans Integrated Service Network (VISN), comprises 3 key components: (1) activation of clinical pharmacy specialists; (2) provider education and targeted notifications and academic detailing; and, (3) patient education.

#### Objectives

We sought to evaluate RaPPID through a cluster-randomized trial of PPI de-prescribing involving 17 VISNs to (1) identifying barriers and facilitators to implementation of RaPPID; and (2) understanding whether the program is effective at improving appropriate use of PPIs and whether there are any unintended consequences, (3) assessing how successfully the program components are delivered, a critical question in understanding why the program did or did not work as intended; and, (4) estimating the costs and possible savings associated with the program and with PPI de-prescribing in general.

#### Methods

We evaluated RaPPID in the context of a nationwide, stratified cluster-randomized controlled trial that incorporated assessments of both effectiveness and implementation (hybrid type II; cluster = VISN). Initially, the dashboard algorithm was validated and evaluated, the dashboard was user-tested and refined (months 1-11), the program was deployed nationally in a cluster-randomized fashion (months 12-24), and subjects were followed for 12 months (months 24-36). In months 18-30, we conducted a process evaluation. Data sources included VA Corporate Data Warehouse (CDW), patient surveys, and interviews with VISN Pharmacy Executives, PBM Academic Detailers, pharmacists, and primary care providers.

#### Impact

This approach allowed us to simultaneously understand barriers and facilitators to implementation of a program focused on stopping use of a specific treatment (de-implementation), share data with VA PBM so they could refine the program to maximize fidelity and consistency of implementation, measure important clinical outcomes, and improve the health of Veterans at scale. The study also provided broader lessons about how to effectively undertake other such nation-wide interventions.

## 1.2 SCHEMA

Months 1-11

Validate PPI Dashboard Algorithm & Test User Interface  
Develop Educational Materials

Randomize

Intervention  
N = 9 VISNs

Control  
N = 8 VISNs

Month 12

Activate VISN Pharmacy Executives, Clinical Pharmacy Specialists & Academic Detailers  
Make Dashboard Available to Intervention Sites

Months 12-24

Electronically Enroll Patients in Dashboard  
Send Baseline Surveys to Patients of 2 VISNs (1 from each arm)

Months 15-27

Send 3-Month Follow-up Surveys to Patients of 2 VISNs (1 from each arm)

Months 24-36

12-month Follow-up of Enrolled Patients

Months 36-42

Data Analyses

## 2 INTRODUCTION

### 2.1 STUDY RATIONALE

Focusing VHA resources more efficiently through de-implementation of low-value care is one of VHA's top 5 strategic priorities. But, to date, large-scale, programmatic initiatives to reduce the use of low-value care had been uncommon (24). This partnered evaluation gave VHA the opportunity to reduce the use of a low-value service, thereby improving the health of Veterans, while also making several key scientific contributions. First, it provided real-time insights into barriers and facilitators of a large-scale de-implementation effort from the perspective of Veterans, providers, and systems. The knowledge gained was "fed back" to our partners in PBM to further enhance future efforts to de-prescribe in other clinical contexts (such as de-prescribing of anti-hypertensives and diabetes medications in older adults) (25). Notably, this was among the largest de-prescribing initiatives ever conducted. Additionally, this is a topic of high priority for our partners at PBM, the VHA GI Program Office, and the Chief Research and Development Officer (CRADO). A second major contribution of the study was the ability to make generalizable conclusions about the risk-benefit ratio of PPI de-prescribing, as well as the true risks posed by PPIs, by virtue of the study's large (VHA-wide) scale, cluster-randomized design, and duration. Prior randomized trials of PPI deprescribing have been relatively small and short in duration, limiting their ability to detect serious but uncommon harms of de-prescribing, such as upper GI bleeding or increased healthcare utilization. Additionally, we planned to rigorously assess the impact of reduced PPI use on selected adverse effects. Whether PPIs truly cause the harms with which they have been associated remains a major unresolved scientific question. Thus, the proposed work aligned well with VHA's broader goal of becoming a Learning Health System and leveraging electronic health record (EHR) data to conduct an evaluation of the planned implementation of a high-priority national clinical program.

### 2.2 BACKGROUND

**Proton pump inhibitors (PPIs) are among the most commonly used medications in the United States.** While these medications are highly effective for acid peptic disorders, observational studies suggest that they can cause harm. Prior studies have reported harms associated with PPI use, including vitamin B12 deficiency, hypomagnesemia, fractures, enteric infections (e.g., *C. difficile* colitis), pneumonia, and myocardial infarctions (1,2). More recent studies have reported additional associations with chronic kidney disease, dementia, stroke, and death (3,9–11).

**Despite data on possible harms, PPIs are overused.** Given the possible harms associated with PPIs, identification of patients unlikely to benefit from long-term daily use is a top priority. The Choosing Wisely® Campaign stated that more than half of those who take PPIs may not need them, and that if gastroesophageal reflux disease (GERD) symptoms resolve after a few weeks, patients should stop their PPIs. Despite such recommendations, preliminary data suggest that >33% of Veterans who use PPIs do not have a clear indication or have well-controlled, uncomplicated GERD. Given that ~15% of Veterans take PPIs chronically, large numbers of Veterans may be incurring harm with little or no benefit.

**Efforts to de-prescribe PPIs have shown efficacy but have failed to be widely adopted.** The data on PPI overuse and harms have generated interest in de-prescribing – "the process of withdrawal of an inappropriate medication, supervised by a healthcare professional with the goal of managing polypharmacy and improving outcomes." (12) De-prescription of PPIs has been evaluated in small trials of patients with GERD. For example, a prospective study conducted at the VA Ann Arbor Healthcare System (VAAAHS) in 2001 evaluated de-prescription in 71 patients with well-controlled GERD. 58% of these 71 patients were successfully de-prescribed at 1 year, but most (73%) required H2-receptor antagonists (H2RAs) or prokinetics for control of symptoms. De-prescription did not reduce quality of life or worsen disease severity (13). In another study of 117 VA patients with well-controlled GERD on twice-daily PPI, 80% were symptom-free 6 months after stepping-down to once-daily dosing (14). Finally, in one VISN, a pharmacy-led program that leveraged clinical pharmacy specialist (CPS) providers, academic detailing, and patient education showed a

reduction in PPI use in an uncontrolled analysis (33% relative reduction in PPI use compared to the average VISN, per PBM), and this reduction has been sustained over several years such that that VISN has the lowest PPI use nationally.

**Stopping PPIs in the wrong patients can cause harm.** By blocking the production of gastric acid, PPIs are highly effective at preventing and treating peptic ulcer disease (PUD) and its complications (e.g., upper gastrointestinal (GI) bleeding and subsequent need for hospitalization, transfusion, endoscopic therapy, surgery). As a corollary, stopping PPIs in patients who are at increased risk for PUD can promote upper GI bleeding, the most common cause of GI hospitalization in the United States. The widespread use of antiplatelet agents for cardiovascular prevention and the growing use of direct anticoagulants means that many Veterans are now at increased risk for upper GI bleeding. Moreover, bleeding is not the only potential unintended consequence of stopping PPIs. A 2017 Cochrane review of randomized trials of PPI de-prescription included 6 studies of de-prescription in patients with PPI-responsive GERD (15). Those randomized to de-prescription followed by on-demand therapy showed a 58% reduction in PPI pill use (3.79 vs 6.57 pills per week), but they also experienced an increase in poor symptom control (RR=1.71; 95% CI: 1.31-2.21). These data suggest that any PPI de-prescribing program must: (1) ensure appropriate de-prescribing – that patients who are taking PPIs for GERD are offered a trial off PPI therapy while those who are at increased risk for GI bleeding are NOT inadvertently taken off their PPIs; and, (2) assess for potential unintended consequences including worsening in upper GI symptoms or quality of life (assessed through patient-reported outcomes (PROs)) and an increase in upper GI bleeding events. Further refinement and validation of an existing electronic algorithm to identify candidates for appropriate de-prescribing was a core deliverable from this study.

**Due to concern about PPI overuse and harms, PBM deployed a national program to appropriately de-prescribe PPIs in 2019-2020.** In light of the data on overuse and PPI harms, PBM deployed a national de-prescribing program in 2019 – the Randomized PPI De-Prescribing (RaPPID) Program. RaPPID was modeled after the successful experience of a VISN program, with modifications to ensure that de-prescribing is appropriate and efficient (using the electronic algorithm developed by our team) and that randomization and deployment was feasible at the national level. Specifically, the program leveraged PBM infrastructure at multiple levels of the health system, including their national network of clinical pharmacy specialist (CPS) providers, an electronic dashboard system, PBM's academic detailing capabilities, and patient education. We worked closely with the Director of Center for Medication Safety at PBM to coordinate the evaluation of RaPPID. PBM's planned de-prescribing program offered a rare opportunity to study the effectiveness of PPI de-prescribing and the barriers and facilitators of a large-scale de-implementation effort.

### 2.2.1 PRELIMINARY WORK

**PPIs are among the most commonly used medications in VHA.** Working with PBM, we examined the prevalence of PPI use in Veterans as well as associated costs. Based on these data, PPIs were used regularly (> 270 days per year) in 15.4% of Veterans. While the cost of these drugs was low on a per-pill basis, their widespread use incurred significant cost – approximately \$50,000,000 per year in direct drug costs alone. At least one-third of Veterans using PPIs had no clear indication or had only uncomplicated GERD. Together, these Veterans (using PPI for no indication or for uncomplicated GERD without risk factors for upper GI bleeding) were the focus of RaPPID.

**PPIs have the potential to cause long-term, debilitating harms.** Multiple PD/PIs Drs. [name] and [name] have published multiple pivotal studies investigating the adverse effects of PPIs (16–20). Although these epidemiological studies cannot definitively address whether these adverse effects are truly caused by PPIs, there are biologically plausible mechanisms linking these potent acid suppressants to a number of physiological changes that could mediate the reported adverse effects. Therefore, PPI therapy in patients without an appropriate indication is a low-value, potentially harmful practice that is not recommended.

**Most patients using PPIs are concerned about adverse effects.** In 2017, co-investigator [name] surveyed 755 patients using PPIs for GERD in an online survey sample (manuscript under review at JAMA-IM). Of these 755 patients, 54% reported awareness of one or more PPI-related adverse effects, most commonly chronic kidney disease (17%), and 78% reported at least some concern about PPI adverse effects. Only 24% reported that a physician had discussed PPI risks and benefits with them, and only 9% had been encouraged to stop by a physician. Independent predictors of a prior attempt to stop included: (1) physician recommendation (OR 3.26, 95% CI: 1.82-5.83); and (2) concern about PPI-related adverse effects (OR 12.0, 95% CI: 6.51-22.2). Notably, patients at high risk of upper GI bleeding, who require long-term PPIs for gastroprotection, were just as likely to have stopped their PPI as others (OR 0.97, 95% CI: 0.66-1.44). This study underscores the prevalence of public concern about PPI-related harms and the potential dangers of self-directed attempts at PPI discontinuation, which could be harmful in the wrong patients.

**Providers are also concerned about PPI-related adverse effects but inappropriately recommend withdrawing PPIs from high-risk patients.** We surveyed a representative sample of internists in the United States (N=487, response rate 53%) to evaluate how physicians were changing their PPI prescribing practices due to concern about adverse effects (21). Of the sample, 63% reported sometimes or often taking steps to reduce their patients' exposure to PPIs by reducing the dose, switching to an H2RA, or stopping the PPI altogether. Providers were also asked to report how likely they would be to recommend PPI de-prescription in a patient with bone loss (a potential PPI adverse effect) in vignettes of patients at low, intermediate, and high risk for upper GI bleeding. Surprisingly, providers were *more likely* to stop PPI in the high-risk vignette (62%) than in the intermediate-risk vignette (47%) or the low-risk vignette (32%). These findings show the importance of having an algorithm that can identify patients who are at high risk for GI bleeding to guide appropriate de-prescribing of PPIs.

**An electronic algorithm can reliably identify candidates for PPI de-prescription in a pilot study.** [name], and co-investigator, [name], have previously used CDW data to identify candidates for PPI de-prescribing. For example, Drs. [name] and [name] developed an electronic algorithm to identify Veterans who had been prescribed PPIs in 2012. They identified ~3,000,000 Veterans who had at least one PPI prescription in the prior year, 33% of whom did not have an appropriate indication. In other work, [name] undertook pilot development and validation of an algorithm to identify appropriate candidates for PPI de-prescribing (i.e., *chronic* PPI users with uncomplicated GERD or without clear indication – the target population for RaPPID) at the Philadelphia VA Medical Center. A CDW-based algorithm was developed to identify candidates for de-prescribing, and validation was performed through manual record review of 100 patients randomly selected from over 9,000 PPI users. The sensitivity of the CDW algorithm for identifying appropriate de-prescribing candidates was 100% (95% CI: 90%-100%), and the specificity was 97% (95% CI: 89%-100%). While these results were impressive, they were obtained at a single center. Additional refinement and validation were performed during our planning period. Given the large number of Veterans using PPIs, it was imperative that the algorithm used to identify de-prescribing candidates in RaPPID have high specificity to prevent alert fatigue and obsolescence among providers.

## 2.3 RISK/BENEFIT ASSESSMENT

### 2.3.1 KNOWN POTENTIAL RISKS

There were no physical risks from participation. The study's chief risk is the psychosocial/financial/legal risk of potential loss of confidentiality. We stored electronic files that contain personal identifiers. The investigative team used their considerable experience in maintaining the confidentiality of large datasets and adhered to all VHA established procedures in place to ensure data confidentiality.

### 2.3.2 KNOWN POTENTIAL BENEFITS

No direct benefits to the subjects themselves were anticipated, as they were not being treated. However, this study's findings directly enhanced all Veterans' care by gaining insights about how to appropriately de-prescribe PPIs and how to

effectively undertake other such interventions to “unlearn” entrenched clinical practices in the future. Thus, the benefit to future VA patients was likely to be substantial.

### 2.3.3 ASSESSMENT OF POTENTIAL RISKS AND BENEFITS

#### Risk Minimization

The risks to subjects were minimal and were addressed by following strict privacy and confidentiality procedures regarding how data are collected, stored, and used throughout the course of this project. There were no physical risks to participation in this study. There was potential risk of psychological, financial, or legal harm due to exposure of personally identifying information (PII) or protected health information (PHI). However, the risk of a breach of confidentiality was low. Throughout the study, VHA, IRB, and HIPAA guidelines were followed to ensure the privacy and integrity of the information collected. Any breach would have been immediately reported to the PD/PIs and the appropriate IRBs. To minimize the risk of a breach of confidentiality, we performed the following steps. First, as soon as the cohort was defined by the data manager, each patient in the cohort was assigned a unique study ID unrelated to any identifying information. We then created a limited access electronic tracking file that mapped the study participant’s identifying information to the study ID.

#### Importance of Knowledge to be Gained

VHA has long been a leader in measuring and delivering high-quality care. In recent years, however, it has become increasingly apparent that efforts to promote quality have inadvertently led to the use of not only high-value, but also low-value care. To date, however, large-scale, programmatic initiatives to reduce the use of low-value care have been uncommon. This partnered evaluation gave VHA the opportunity to simultaneously address the use of a low-value clinical service and to understand multi-level barriers to de-implementation of a commonly prescribed medication. Additionally, by randomizing the program, VHA ensured that efforts to de-prescribe PPIs do not cause unintended harms (such as upper GI bleeding) and assess the effect of reduced PPI use on selected adverse effects (such as enteric infections, fractures, pneumonia, and hypomagnesemia). Notably, this was the largest de-prescribing initiative ever conducted. Studying its effects in real time yielded valuable generalizable knowledge about how systems can effectively de-implement low-value care. Moreover, the randomized evaluation yielded clinical knowledge about the balance of benefit and harm for PPIs, knowledge that was unlikely to be acquired in any other evaluation.

## 3 PRIMARY OBJECTIVES AND ENDPOINTS

OBJECTIVES	ENDPOINTS	JUSTIFICATION FOR ENDPOINTS
Primary		
Proportion of days PPIs are prescribed at or above the baseline daily dosing-frequency, over the 12 months following the index visit.	We hypothesize (H1) that the proportion of days will be lower in intervention group than in the control group (i.e., that the outcome will be superior in the intervention vs control group). This outcome is analogous to the medication possession ratio.	This is the appropriate measure of success of de-prescribing because it captures a variety of results in a single endpoint, including discontinuation without resumption, discontinuation with intermittent or on-demand use, and resumption of daily PPI at or above baseline dosing frequency.

## 4 STUDY DESIGN

### 4.1 OVERALL DESIGN

**Study Design:** We evaluated RaPPID in the context of a nationwide, stratified cluster-randomized controlled trial that incorporated assessments of both effectiveness and implementation (hybrid type II) (28). RaPPID was a multi-level de-prescribing program modeled after a similar initiative developed and deployed in one VISN in 2015. After validating and testing the deprescribing algorithm and dashboard, developing educational materials and randomization (months 1-11), the program was deployed nationally in a cluster-randomized fashion (months 12-24). During the randomization and subsequent follow-up period (months 24-36), we assessed the program's impact on a variety of clinical outcomes.

**Study Population and Sample:** De-prescribing of PPIs has potential clinical and economic benefits (by reducing unnecessary daily use of a medication with possible long-term harms). However, de-prescribing may also be harmful due to worsening upper GI symptoms and increased risk of upper GI bleeding. To maximize potential benefit and minimize potential harm, RaPPID focused on “chronic PPI users” (defined as daily PPI for  $\geq$  90 days during the 120-day period prior to PCP visit) with uncomplicated GERD, OR with no clear indication for PPI. Those who had acceptable indications for chronic PPI therapy (e.g., NSAID use, anti-thrombotic use, PUD, Barrett’s esophagus, erosive esophagitis, eosinophilic esophagitis) were excluded. Identification of candidates for appropriate de-prescription was facilitated by a high-specificity electronic algorithm, as discussed in Section 2.2, Background.

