### Chronic PPI Users

Defined as: ≥90-day prescription during the 120-day period prior to a scheduled primary care visit

Patients Who Take PPIs	
Once Daily Meeting any of the following criteria:	Twice Daily Meeting any of the following criteria:

■ No clear indication for PPIs

■ Uncomplicated GERD (i.e., no erosive esophagitis, stricture, dysphagia, or Barrett's esophagus)

	

■ No clear indication for PPIs

■ Any indication (except Zollinger-Ellison)

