## 5.2 EXCLUSION CRITERIA

The RaPPID Program avoided de-prescribing PPIs in patients for whom chronic PPI therapy was recommended by guidelines, consensus statements, and/or expert opinion. Stopping PPIs in these patients could have caused harms such as upper GI bleeding. Patients taking PPIs were excluded from the dashboard if they had one or more of the characteristics listed in the table below.

Twice-daily PPI Users with Zollinger-Ellison	
Once-daily PPI Users with any the following characteristics:	

■ Eosinophilic esophagitis

■ Esophagitis

■ Barrett's esophagus

■ Peptic ulcer

■ Zollinger-Ellison

■ Idiopathic pulmonary fibrosis

	

■ Pancreatic enzyme replacement

■ Esophageal ulcer

■ Esophageal stenosis/stricture

■ Dysphagia (other than oropharyngeal)

OR	
NSAID Users Meeting any of the following criteria:	Low-dose Aspirin Users Meeting any of the following criteria:

■ age > 65 years of age

■ Take a 2nd NSAID

■ Take daily aspirin

■ Take an anti-thrombotic drug

■ Take an oral steroid

	

■ age <math>\geq</math> 60 years of age

■ Take NSAIDs regularly

■ Take an anti-thrombotic drug

■ Take a corticosteroid

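### Sections 4.1 and 2.2.1 describe anti-thrombotic users as excluded, but the 5.1–5.2 dashboard rule lists once-daily patients on a non-aspirin anti-thrombotic alone for PPI taper and discontinuation

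*Combined protocol and SAP*

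**What the plan says.** Two places in the combined protocol and SAP describe the population in general terms. In 4.1 (Overall Design), the exclusion sentence begins "Those who had acceptable indications for chronic PPI therapy (e.g., NSAID use, anti-thrombotic use, PUD", goes on to esophageal diagnoses, and says these patients were excluded. Anti-thrombotic use stands there without a qualifier. In 2.2.1 (Preliminary Work), the program's focus is given as Veterans "using PPI for no indication or for uncomplicated GERD without risk factors for upper GI bleeding".

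The detailed rule is in 5.1 and 5.2. For once-daily users, 5.1 admits anyone with no clear indication, or with "Uncomplicated GERD (i.e., no erosive esophagitis, stricture, dysphagia" or Barrett's esophagus. In 5.2 the operative sentence is "Patients taking PPIs were excluded from the dashboard if they had one or more of the characteristics listed in the table below". The table lists diagnoses (plus pancreatic enzyme replacement) for once-daily users, and then two drug columns, one for NSAID users and one for low-dose aspirin users. The entry "Take an anti-thrombotic drug" appears once in each drug column, as a co-factor. No row excludes anti-thrombotic use by itself.

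Section 4.1.1 sets the regimen for once-daily users: two weeks of alternate-day dosing, then stop. Section 4.1.2 recommends de-prescribing for patients who meet the inclusion and exclusion criteria.

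**The concern.** The protocol itself treats this group as one to protect. Section 2.2 names antiplatelet agents and says the "growing use of direct anticoagulants means that many Veterans are now at increased risk for upper GI bleeding". It then requires of any de-prescribing program that "those who are at increased risk for GI bleeding are NOT inadvertently taken off their PPIs". The electronic algorithm is the planned means of doing so.

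Two things are at stake. The first is patient safety: if the dashboard ran on 5.2 as written, patients whom 4.1 describes as having an acceptable reason for long-term PPI use were put forward for stopping it. The second is interpretation. Section 7.2.1 makes complications of peptic ulcer disease, bleeding included, a secondary outcome, and section 8 hypothesizes no important rise in upper GI complications. A reader who takes the population from 4.1 or 2.2.1 would attach those results to patients at lower bleeding risk than 5.2 admits.

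**Working it through.** The plan gives no figure to reproduce; the check is one of logic.

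**Step 1. The 5.2 rule.** Take a once-daily user with none of the listed diagnoses and no pancreatic enzyme replacement. The drug columns exclude the patient if either condition holds:

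- A: NSAID use AND (age > 65, OR a second NSAID, OR daily aspirin, OR an anti-thrombotic, OR an oral steroid)
- B: low-dose aspirin use AND (age ≥ 60, OR regular NSAIDs, OR an anti-thrombotic, OR a corticosteroid)

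**Step 2. Anti-thrombotic alone.** With no NSAID, A is false whatever follows in its bracket. With no aspirin, B is false in the same way. Age, the anti-thrombotic and any steroid enter only inside those brackets, so none of them can exclude the patient. An 85-year-old on an anticoagulant and a steroid, with no NSAID or aspirin, is not excluded.

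**Step 3. Does 5.1 close the gap?** Uncomplicated GERD is defined by the absence of esophageal complications, with no condition on bleeding risk. The once-daily criteria are joined by any-of, so meeting the GERD criterion is enough. The no-clear-indication route is less certain, because 5.1 does not say whether anti-thrombotic use would count as an indication. The GERD route does not depend on that.

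**Step 4. Side by side, once-daily users.**

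| Drug use | 4.1 as worded | 5.2 as written |
|---|---|---|
| Anti-thrombotic with an NSAID | excluded | excluded |
| Anti-thrombotic with low-dose aspirin | excluded | excluded |
| Non-aspirin anti-thrombotic alone, any age | excluded | eligible |
| Single NSAID, age 65 or younger, no listed co-factor | excluded | eligible |

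**Step 5. Which differences matter.** The fourth row comes from an age- and co-factor-graded NSAID rule. Such grading makes sense only if lower-risk NSAID users were meant to remain eligible, so it looks deliberate, and 4.1 merely states it too broadly. The same applies to aspirin-only users under 60 if aspirin is read as an anti-thrombotic in 4.1. The third row has no such grading: no age or co-factor limit applies to it.

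**Step 6. Twice-daily users.** 5.1 admits "Any indication (except Zollinger-Ellison" disease). These patients step down to once daily and stay on a PPI, so the conflict over stopping does not arise for them.

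**The case against.** The strongest reply is that 4.1 is a one-sentence overview introduced by e.g., that 2.2.1 is preliminary work describing a focus, and that a reader who wants the criteria will go to 5.1–5.2. This is fair as to which text governs. It does not remove the conflict: e.g. makes the list incomplete, but a named example should still be true, and 2.2.1 separately gives the stricter description.

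A second reply is that the 5.2 table was extracted from PDF and a row could have been lost. Both drug columns look complete and nothing suggests a missing block. Still, the point rests on the absence of a row, which is one reason to check the query first.

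A third is that aspirin may be the anti-thrombotic meant in 4.1. The 5.2 columns list anti-thrombotics separately from aspirin, and the anticoagulant-only patient stays eligible on either reading.

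Stronger readings are tempting, and the documents do not support them:

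- *Patients on anticoagulants were taken off PPIs.* Pharmacists and PCPs decided, and no listed or stopped patient of this kind is shown.
- *Clinicians would have failed to catch them.* In the internist survey in 2.2.1, 62% would stop in the high-risk vignette against 32% in the low-risk one. But those vignettes concern a patient with bone loss, the protocol does not equate high risk with anti-thrombotic use alone, and RaPPID adds PCP education and trained pharmacists. The survey explains why the algorithm matters; it does not show that review failed here.
- *The arm comparison is biased.* One set of criteria is stated for both arms.
- *The trial claims proven bleeding safety.* The numbered non-inferiority hypotheses cover outpatient utilization (H2) and upper GI symptoms (H3), and these documents report no bleeding result.

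**Conclusion.** The point holds, limited to once-daily users on a non-aspirin anti-thrombotic with no NSAID and no aspirin. As written, 4.1 and 2.2.1 on one side and 5.1–5.2 on the other cannot both describe who was eligible, and the difference falls on a bleeding-risk group that section 2.2 says must be protected. It should be resolved because it bears on safety and on the population behind the GI-complication results.

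The size cannot be stated. The documents give no count or share of candidates on an anti-thrombotic alone, and the number is zero if the query in fact excluded them. The conclusion assumes that the 5.2 table is complete as it appears and that the dashboard followed it. The primary comparison is not shown to be affected.

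**What to change.** First, check which rule the dashboard query applied.

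**If it applied 5.2:**
- Correct 4.1 and 2.2.1 to state the 5.2 criteria, including the graded NSAID and aspirin rules.
- Keep every enrolled patient in the ITT analysis.
- Report serious GI complications by arm, as descriptive counts and rates, for the anti-thrombotic-only group from existing CDW data. Label the table post hoc, and note that over-the-counter NSAID or aspirin use may be missed, so some patients classed as anti-thrombotic-only may have been taking these drugs too.
- If 4.1 states the clinical intent, add stand-alone anti-thrombotic use to the 5.2 exclusions before any further use of the dashboard.

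**If the query already excluded these patients:** correct 5.2 instead; the table is then unnecessary.

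The cost is one look at an existing query, a wording correction and at most one descriptive table. No new data are collected, and nobody's enrollment or analysis status changes.
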